4.2 Exclusion Criteria

Subjects who meet any of the following criteria will be excluded from participation in the study:

1. Evidence of clinically significant hematologic, renal, endocrine, pulmonary, cardiac, gastrointestinal (GI), hepatic, psychiatric, neurologic, immunologic, allergic disease (including multiple or clinically significant drug allergies), or any other condition that, in the opinion of the Investigator, might significantly interfere with the absorption, distribution, metabolism, or excretion of study drug, or place the subject at an unacceptable risk as a participant in this study;
2. History of malignancy (other than successfully treated basal cell or squamous cell skin cancer);
3. History or presence of an abnormal ECG that, in the opinion of the Investigator, is clinically significant;
4. Laboratory results (serum chemistry, hematology, coagulation, and urinalysis) outside the normal range at screening and Check-in and considered clinically significant in the opinion of the Investigator. Any elevation of aspartate transaminase (AST) and alanine transaminase (ALT) above the upper limit of normal at screening and/or Check-in is exclusionary. One retest of an exclusionary laboratory result is allowed at the discretion of the Investigator;
5. Has had an acute illness considered clinically significant by the Investigator within 30 days prior to screening;
6. History of alcoholism or drug abuse within 2 years prior to screening;
7. Has used any product containing nicotine within 90 days prior to screening or intends to use any product containing nicotine during the course of the study;
8. Has had any immunizations (live vaccines) in the 4 weeks prior to screening;
9. Has used medications that affect GI motility or gastric emptying; such as metoclopramide, proton pump inhibitors, and H2 blockers; within 30 days prior to Day 1;
10. Has used any prescription or over-the-counter medication (with exception of acetaminophen), vitamins/herbal supplements (with the exception of hormonal contraceptives) within 14 days prior to Day 1;
11. Has used any other study drug within 30 days or 5 half-lives of the drug (whichever is longer) prior to Day 1;
12. Has lost or donated >450 mL of whole blood or blood products within 30 days prior to screening;

13. Investigator has reason to believe that the subject may be unable to fulfill the protocol visit schedule or requirements;
14. Has any finding that, in the view of the Investigator or Medical Monitor, would compromise the subject's safety requirements; or
15. Is employed by the Sponsor, the Contract Research Organization (CRO), or the study site (permanent, temporary contract worker, or designee responsible for the conduct of the study), or is a family member (spouse, parent, sibling, or child) of the Sponsor, CRO, or study site employee.

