3 STUDY DESCRIPTION

3.1 Summary of Study Design

This is a Phase 1, open-label, single-ascending dose study to evaluate the safety, tolerability, and PK of OP-101 after SC administration in up to 8 healthy subjects at 1 site in Australia.

This study will consist of a 21-day Screening Period, a 2-day Treatment Period, and Follow-up Visits on Days 8 and 15. Subjects will sign an informed consent form (ICF) before any study procedures are performed and must meet all of the inclusion and none of the exclusion criteria to participate in the study. Eligible subjects will be admitted to the investigational site on Day -1, dosed on Day 1, and discharged on Day 3.

[figure not shown]
Figure 1 presents the cohort dosing schematic. There will be 2 separate and sequential SC cohorts (4 mg/kg and 8 mg/kg) with 4 subjects in each cohort who complete Day 15. Cohort 1 will enroll 4 subjects administered a single SC dose of 4 mg/kg. Dose escalation from Cohort 1 (4 mg/kg) to Cohort 2 (8 mg/kg) will be determined by the safety review committee (SRC), consisting of the Medical Monitor, the Principal Investigator (or delegate), and Sponsor representative after review of safety, tolerability, and any available PK data through Day 8 of Cohort 1. Cohort 2 will enroll 4 subjects administered a single SC dose of 8 mg/kg.

During the Treatment Period, plasma and urine samples will be collected for PK analysis. Plasma PK samples will be collected predose, at 30 minutes and at 1, 2, 4, 6, 8, 10, 12, 16, 24, and 30-36 hours after dosing, as well as on Day 3 (~48 hr). Blood samples for PK analysis can be obtained within ± 5 minutes of the scheduled sampling time for sample times ≤ 1 hour, within ± 10 minutes of the scheduled sampling time for sample times ≤ 12 hours, and within ± 2 hours of the scheduled sampling times for sample times > 12 hours.

Urine PK samples will be collected predose (spot sample) and between 0 to 4, 4 to 8, 8 to 12, 12 to 18, 18 to 24, and 24 to 48 hours.

Safety assessments will include adverse event monitoring, clinical laboratory tests (hematology, chemistry, and urinalysis), physical examinations, and vital signs (pulse rate, blood pressure [BP], respiration rate, and temperature). Coagulation testing will be performed at screening. Pregnancy testing will be performed at screening and Day -1.

Figure 1. OP-101 Single-Ascending Subcutaneous Dose Schedule – Day 1

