5.6 Prior and Concomitant Medications and/or Procedures

5.6.1 Excluded Medications and/or Procedures

Subjects who have lost or donated >450 mL of whole blood or blood products within 30 days prior to screening will be excluded.

See Section 4.2 for exclusion criteria.

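### The live-vaccine and blood-loss exclusions (and, in part, the acute-illness exclusion) stop counting at screening, so no dated rule covers these events between screening and Day 1.

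*Protocol*

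**What the plan says.** Protocol section 4.2 uses two anchors in one list.

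- **Anchored to screening.** Exclusion 5: "Has had an acute illness considered clinically significant by the Investigator within 30 days prior to screening". Exclusion 8: "Has had any immunizations (live vaccines) in the 4 weeks prior to screening". Exclusion 12: "Has lost or donated >450 mL of whole blood or blood products within 30 days prior to screening". Section 5.6.1 repeats the last of these with the same anchor: "Subjects who have lost or donated >450 mL of whole blood or blood products within 30 days prior to screening will be excluded".
- **Anchored to Day 1.** Exclusion 9 (drugs acting on gastrointestinal motility), exclusion 10 (other medication, "within 14 days prior to Day 1") and exclusion 11: "Has used any other study drug within 30 days or 5 half-lives of the drug (whichever is longer) prior to Day 1".

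On timing, section 3.1 states: "This study will consist of a 21-day Screening Period, a 2-day Treatment Period, and Follow-up Visits on Days 8 and 15". Section 6.1 allows the Screening Visit on any day from -21 to -1; the schedule table in Appendix A gives Days -21 to -2.

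Appendix A and the SAP schedule table mark the inclusion/exclusion criteria a second time at Check-in (Day -1). Protocol section 6.2, which lists the Check-in procedures, does not include that step.

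**The concern.** A look-back window normally protects the period just before dosing. Here three windows close at the Screening Visit, which can be three weeks earlier. The written rule then excludes an older event and admits a more recent one of the same kind. Repeating the eligibility check on Day -1 does not help, because a rule that counts back from screening cannot reach anything after screening.

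The protocol closes this kind of gap elsewhere. Exclusion 7 (nicotine) also counts from screening, but it adds intended use during the study, and cotinine is retested at Check-in. Exclusion 4 and inclusions 10 and 13 name both screening and Check-in. Exclusions 5, 8 and 12 have no such extension, and no reason is given.

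At stake is the interpretability of the data for the primary objective, safety and tolerability. The study is open-label, has no control arm and has 4 subjects per cohort. A recent vaccination, blood loss or illness could produce symptoms or laboratory changes that overlap with the post-dose period. The kidney markers are the most exposed. Footnote 6 of the schedule gives KIM-1 and NGAL one pre-dose sample, on Day -1, and SAP section 7.4.2 uses Day -1 as the laboratory baseline. Section 1.2 of the protocol names renal function as the thing to watch.

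**Working it through.** **Inputs.** Look-back L: 30 days for illness (exclusion 5), 4 weeks = 28 days for live vaccine (exclusion 8), 30 days for blood loss (exclusion 12, section 5.6.1). Screening day: -21 to -1 (section 6.1) or -21 to -2 (Appendix A).

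**Check of the stated period.** The schedule runs from Day -1 to Day 1 with no Day 0, so Day -k is k days before dosing. Days -21 to -1 make 21 days, which reproduces the stated 21-day Screening Period. Days -21 to -2 make 20.

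**Formula.** For screening s days before dosing, a screening-anchored rule covers s to s + L days before dosing. The elapsed time from screening to dosing is s days, with s - 1 whole calendar days in between.

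| Screening day | Illness and blood loss: days before dosing covered | Live vaccine: days before dosing covered | Elapsed days to dosing | Whole days in between |
|---|---|---|---|---|
| -21 | 21 to 51 | 21 to 49 | 21 | 20 |
| -14 | 14 to 44 | 14 to 42 | 14 | 13 |
| -7 | 7 to 37 | 7 to 35 | 7 | 6 |
| -2 | 2 to 32 | 2 to 30 | 2 | 1 |
| -1 | 1 to 31 | 1 to 29 | 1 | 0 |

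The gap is therefore about 20 days at most and 1 to 2 elapsed days when screening is late.

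**The inversion, for screening on Day -21.**

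- Blood loss above 450 mL on Day -45 falls within 21 to 51 and excludes. On Day -10 it does not.
- A live vaccine on Day -48 falls within 21 to 49 and excludes. On Day -18 it does not.
- A clinically significant illness on Day -50 meets exclusion 5. One on Day -6 that has settled by Check-in does not meet that criterion.

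**Overlap with exclusion 10.** If a vaccine counts as a medication, exclusion 10 covers Day -14 to Day -1. The vaccine gap for a Day -21 screen then shrinks from Days -20 to -1 (20 days) to Days -20 to -15 (6 days). The protocol does not say whether it counts.

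**With the windows run through Day 1.** For a Day -21 screen, coverage becomes 0 to 51 days for illness and blood loss (21 + 30) and 0 to 49 days for live vaccine (21 + 28). The gap is 0.

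**The case against.** The strongest reply is that these events do not simply go unnoticed, and much of it stands.

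- **Illness.** Adverse events are recorded from consent (section 8.1) and assessed at Check-in, along with physical examination, vital signs, safety laboratory tests and medication review (section 6.2). Inclusion 4, exclusions 1, 4 and 14 and the intercurrent-illness reason in section 4.3 all allow the Investigator to act. Exclusion 5 itself depends on the Investigator's judgment, so calling the others discretionary does not set them apart. An illness treated with anything other than acetaminophen in the last 14 days would also meet exclusion 10. A reader might infer that a recent illness passes the protocol as a whole. The documents do not support that; only the dated rule has the gap.
- **Hematology.** A reader might infer that the hematology baseline rests on one reading. SAP section 7.4.2 does define baseline as Day -1, but protocol section 8.6 also schedules screening and Day 1 pre-dose samples, so a transient shift could be seen. The single-reading point holds for KIM-1 and NGAL, and for urinary albumin and creatinine as listed in section 6.
- **Escalation.** A reader might infer that one or two such subjects could change the escalation decision. The rule in section 3.2 counts only drug-related events and pauses dosing pending review. Section 8.1.3 reserves a related judgment for events with no other identifiable cause, and a recorded illness would be such a cause. No probability of such an event can be derived from the documents.
- **Blood volume.** There are 13 scheduled plasma PK draws, but no draw volumes are given, so the added burden of a prior blood loss cannot be sized.

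It can also be said that exclusions 9 to 11 are drug washouts, naturally tied to dosing, while 5, 8 and 12 are history items, naturally tied to the visit at which history is taken. That may explain the split, but the protocol does not say so, and it does not justify admitting the newer event. The reply is weakest for vaccination and blood loss: medication review may record a vaccine without excluding it, and no listed Check-in step asks about donation.

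**Conclusion.** The point holds as an inconsistency in eligibility wording. It is firm for exclusions 8 and 12 with section 5.6.1, and weaker for exclusion 5, where judgment-based safeguards remain. The uncovered interval depends on the screening day; the upper figure of about 20 days applies only to a subject screened on Day -21. For vaccines it may be as short as 6 days in that case if exclusion 10 applies.

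The consequence is limited to possible confounding of safety data and of the single Day -1 KIM-1/NGAL baseline. With 4 subjects, one affected subject is 1/4 = 25% of a cohort; that is a proportion, not an estimate of effect. Sample size is unaffected, since it rests on practical considerations rather than power. The conclusion assumes the criteria are applied as written and that an event of this kind occurs in the interval; the documents give no rate for that.

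**What to change.** Reconcile the anchors in section 4.2. Extend exclusions 5, 8 and 12, and the matching sentence in section 5.6.1, so that each existing window runs back the sponsor's stated time from screening and also forward to Day 1. This keeps the durations and everything now excluded. Add the eligibility review to section 6.2, where the schedule tables already imply it, and have the site ask about acute illness, live vaccination and blood loss since screening. State whether a vaccine counts as a medication under exclusion 10. If the difference in anchors is intended, the sponsor should give the reason instead.

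The cost is a wording amendment and three questions on Day -1. The downside is an occasional late exclusion; section 4.3 already provides for replacing subjects withdrawn before dosing.

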4.3 Withdrawal Criteria

Participation of a subject in this clinical study may be discontinued for any of the following reasons:

- The subject withdraws consent or requests discontinuation from the study for any reason;
- Occurrence of any medical condition or circumstance that exposes the subject to substantial risk and/or does not allow the subject to adhere to the requirements of the protocol;
- Any SAE, clinically significant adverse event, severe laboratory abnormality, intercurrent illness, or other medical condition which indicates to the Investigator that continued participation is not in the best interest of the subject;
- Pregnancy;
- Requirement of prohibited concomitant medication;
- Subject failure to comply with protocol requirements or study-related procedures;
- Termination of the study by the Sponsor or the regulatory authority; or
- Subject noncompliance.

If a subject withdraws prematurely from the study due to the above criteria or any other reason, study staff should make every effort to complete the full panel of assessments scheduled for the Early Termination Visit. The reason for subject withdrawal must be documented in the electronic case report form (eCRF).

If a subject is withdrawn from the study due to an adverse event, the subject will be asked to return to the site for, at a minimum, the evaluations scheduled for the Early Termination Visit. If the adverse event has still not resolved, additional follow-up will be performed, as appropriate, based on the Investigator's judgment, and documented in the subject's medical records. As a minimum requirement, SAEs should be followed for 30 days after the subject's last dose of study drug.

Withdrawn subjects will be replaced if the subject is withdrawn prior to dosing. Withdrawn subjects may be replaced after dosing if adequate PK data is not available for that subject at the discretion of the Investigator and Medical Monitor.

5 STUDY TREATMENTS

5.1 Treatment Groups

There will be 2 separate and sequential SC cohorts with 4 subjects in each cohort. The population will include healthy men and women aged 18 to 65 years, inclusive.

Dose escalation from Cohort 1 to Cohort 2 will be determined by the SRC, consisting of the Medical Monitor, the Principal Investigator (or delegate), and Sponsor representative after review of safety, tolerability, and any available PK data through Day 8 of Cohort 1.

Dosing with OP-101 is planned for the cohorts as follows:

- Cohort 1: Single SC dose of 4 mg/kg, and
- Cohort 2: Single SC dose of 8 mg/kg.

5.2 Rationale for Dosing

The safety of OP-101 is supported by the completed Phase 1 IV dosing study in healthy volunteers at 20 and 40 mg/kg (3-5 fold higher than the planned SC doses in this study). In addition, a series of nonclinical studies previously conducted with the active agent in OP-101, NAC, and numerous clinical studies that have been performed with NAC provide further support for the proposed dosing. The overall toxicological profile of OP-101 is expected to be comparable to NAC, which has been evaluated in nonclinical toxicity studies in support of the approval of Acetadote.

Good Laboratory Practice toxicology studies conducted with OP-101 in juvenile and adult rats, incorporating repeat IV doses up to 2000 mg/kg or single IV doses up to 1000 mg/kg, have shown no adverse clinical signs or mortality. The predominant finding in the toxicology studies was microscopic changes in the kidney that were generally localized to the proximal tubule. The findings included tubular degeneration/regeneration, mineralization, basophilic granules/tubules, and/or single cell necrosis, which increased in severity with increasing dose. While a defined NOAEL was not identified in the repeat-dose studies, the single-dose study in adult male rats, demonstrated a NOAEL of 200 mg/kg based upon the absence of single cell necrosis by 2 weeks after dosing and minimal-to-mild severity of this finding noted at earlier time points. Of note, no effects were observed for urinalysis or urine chemistry parameters, and no changes in other urinary biomarkers (kidney injury molecule-1, neutrophil gelatinase-associated lipocalin, albumin, cystatin C, and β -microglobulin) were detected.

From the completed IV dosing study in healthy volunteers it was determined that the clearance of OP-101 was rapid with no detectable drug in the plasma after 24 hours. There were also no clinical adverse events in subjects administered IV doses of 20 or 40 mg/kg OP-101. To enable chronic dosing, SC dosing is being evaluated in this study. The SC dosage formulation has been optimized to enable a single SC dose of 400-500 mg. Higher doses may require two SC injections to achieve the desired dose if necessary. The selection of 4 and 8 mg/kg SC doses enable the majority of the subjects to receive only one injection and is 3-5 fold lower dose than the previous IV study in healthy volunteers. Exposure to NAC at the proposed starting dose and subsequent dose cohorts in this study is orders of magnitude less than that demonstrated to be safe in humans following oral or IV administration.

5.3 Randomization and Blinding

This open-label study consists of 2 separate and sequential SC cohorts. Randomization and blinding methods will not be used in this study.

Cohort 1 will enroll 4 subjects administered a single SC dose of 4 mg/kg. Dose escalation from Cohort 1 (4 mg/kg) to Cohort 2 (8 mg/kg) will be determined by the safety review committee (SRC), consisting of the Medical Monitor, the Principal Investigator (or delegate), and Sponsor representative after review of safety, tolerability, and any available PK data through Day 8 of Cohort 1. Cohort 2 will enroll 4 subjects administered a single SC dose of 8 mg/kg.

If an eligible subject is not used in the first cohort and is outside the screening window for a future cohort, the subject may be rescreened.

5.4 Breaking the Blind

This is an open-label study. Study drug assignment will be known by subjects, investigational site staff, and the Sponsor.

5.5 Drug Supplies

5.5.1 Formulation and Packaging

OP-101 study drug is provided as lyophilized powder in Schott Glass, 5 cc/13 mm Type 1 clear glass vials with West, 13 mm, single vent lyophilizer grey butyl chloride stoppers, and West 13 mm flip-top matte white caps. Each vial is filled to deliver 500 ± 50 mg OP-101. Each vial is reconstituted 0.7 mL sterile water for injection to yield 400 mg/mL OP-101 in 20 mM histidine, pH 5.5 and 80 mg/mL trehalose. Vials of study drug will be supplied in boxes labeled for this study. Vials will be reconstituted with sterile water for injection prior to use.

OP-101 will be stored at 2 to 8°C and must not be frozen. Reconstituted OP-101 is stable at room temperature for up to 7 days if the vial seal is not compromised.

5.5.2 Study Drug Preparation and Dispensing

Trained and qualified site personnel will administer OP-101 to subjects within the clinical facility. Site personnel should ensure that the study drug is stored in accordance with the environmental conditions (temperature, light, and humidity) as determined by Orpheris and outlined in the Pharmacy Manual. Instructions for OP-101 preparation are documented in the pharmacy manual.

5.5.3 Study Drug Administration

Study drug will be administered on Day 1 as a SC injection under the supervision of the site personnel.

Dose Escalation

Cohort 1 will enroll 4 subjects administered a single SC dose of 4 mg/kg. Dose escalation from Cohort 1 (4 mg/kg) to Cohort 2 (8 mg/kg) will be determined by the safety review committee (SRC), consisting of the Medical Monitor, the Principal Investigator (or delegate), and Sponsor representative after review of safety, tolerability, and any available PK data through Day 8 of Cohort 1. Cohort 2 will enroll 4 subjects administered a single SC dose of 8 mg/kg.

5.5.4 Treatment Compliance

Study drug will be administered at the investigational site by site staff.

5.5.5 Storage and Accountability

Study drug will be stored in a secure, temperature-controlled location. Study drug will only be prepared and dispensed by authorized site personnel at the clinical site.

Documentation will be performed for the receipt, storage, dispensing, and retention of study drug during the conduct of study to ensure complete accountability. Used study drug vials will be retained for monitoring purposes.

5.6 Prior and Concomitant Medications and/or Procedures

5.6.1 Excluded Medications and/or Procedures

Subjects who have lost or donated >450 mL of whole blood or blood products within 30 days prior to screening will be excluded.

See Section 4.2 for exclusion criteria.

5.6.2 Restricted Medications and/or Procedures

Subjects are not permitted to take prescription or non-prescription drugs (including vitamins and dietary or herbal supplements) within 14 days (14 days if the drug is a potential enzyme inducer) or 5 half-lives (whichever is longer) prior to the first dose of study medication until completion of the Day 15 Follow-up Visit, unless, in the opinion of the Investigator and Sponsor, the medication will not interfere with the study or is required out of medical necessity.

See Section 4.2 for exclusion criteria.

5.6.3 Restricted Cigarette Use

Subjects are not permitted to use any product containing nicotine during the course of this study and may not have used any product containing nicotine within 90 days prior to screening.

5.6.4 Permitted Medications

Nonsteroidal anti-inflammatory drugs (eg, ibuprofen or naproxen) may be considered for use during the study on a case-by-case basis by the Investigator in consultation with the Orpheris Medical Monitor if required.

Hormonal contraception (oral, implant, injection, ring, or patch) for at least 12 weeks before the Screening Visit is permitted.

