1.2 Risk/Benefit

This study is a follow up to the completed Phase 1 single ascending IV dosing study in healthy volunteers. In the completed Phase 1 study, treatment with a single IV dose of OP-101 at 20 and 40 mg/kg was generally well tolerated in healthy subjects based on an assessment of clinical and laboratory adverse events. There were no clinically meaningful changes from baseline in laboratory parameters except changes in the urinalysis parameters of proteinuria and the presence of granular urinary casts. Transient elevations in KIM-1 and NGAL were observed, and subjects who experienced an increase in KIM-1 or NGAL at Day 15 underwent additional follow-up, at the recommendation of the SRC. The additional measurements in either KIM-1 or NGAL were

conducted as a precautionary measure and the values subsequently returned to baseline. There were no clinically meaningful changes in vital signs or ECGs. OP-101 has also been tested in nonclinical studies with no adverse clinical changes observed across multiple species and models. The anticipated risks associated with OP-101 may be categorized as potentially related to the PAMAM dendrimer and/or NAC. In vitro studies have demonstrated that the dendrimer is not systemically metabolized in human hepatocytes or human plasma and is rapidly cleared by the kidney. Good Laboratory Practice toxicity studies with repeat dosing of OP-101 in juvenile and adult rats have shown partial dose-dependent changes of proximal tubular cells characterized by mild intracellular basophilia and mild single-cell necrosis, but no associated clinical adverse events, mortality, or change in electrolytes. Toxicology studies in rats with single-doses of OP-101 have demonstrated resolution of the single-cell necrosis by 2 weeks postdosing and no adverse clinical observations or changes in urinalysis parameters. In summary, the renal clearance of OP-101 and the effects on proximal tubular cells in nonclinical studies indicate that renal function should be carefully assessed in human studies.

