#### ***7.4.2 Clinical Laboratory Tests***

The clinical laboratory tests will include Hematology and Coagulation, Chemistry, and Urinalysis at Screening and other time points as specified in Appendix Table 1.

Observed values from Baseline and each time point, as well as change from Baseline to each time point will be summarized descriptively based on Safety Population by Treatment. Baseline is defined as reading on Day -1 (Check-in). If the reading on Study Day -1 is missing, the last reading before dosing will be used as baseline. A summary table representing abnormal value of safety laboratory tests will also be presented. Additional Urinary biomarkers include albumin, creatinine, KIM-1, and NGAL will also be listed and summarized similarly.

Tests for HIV, HBsAg, and HCVab will be completed at the Screening Visit to determine eligibility. The data will be listed by treatment for Safety Population. Coagulation test including aPTT, PTT, INR will be completed at the Screening visit, and the data will be listed by treatment for the Safety Population.

An FSH test will be performed at Screening for women who are post-menopausal, with amenorrhea for at least 2 years.

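### The SAP does not link renal safety values to NSAID use, which protocol 5.6.4 allows for, and its concomitant-medication window closes at about 48 hours although renal follow-up runs to Day 15

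*Protocol*

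**What the plan says.** Protocol 1.2 reports proteinuria and granular casts after IV OP-101, and adds: "Transient elevations in KIM-1 and NGAL were observed". It describes proximal tubular changes in rats and concludes that these, with renal clearance of the drug, "indicate that renal function should be carefully assessed in human studies". Protocol sections 6.2 to 6.6 and 8.6 and Appendix A accordingly schedule eGFR, KIM-1, NGAL, urinary albumin and urinalysis at Check-in, Days 2, 3, 8 and 15, and early termination.

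Three protocol passages govern other medication:
- 5.6.2 bars prescription and non-prescription drugs until the Day 15 visit, unless the Investigator and Sponsor consider that "the medication will not interfere with the study or is required out of medical necessity".
- 5.6.4 says: "Nonsteroidal anti-inflammatory drugs (eg, ibuprofen or naproxen) may be considered for use during the study on a case-by-case basis". The decision lies with the Investigator in consultation with the Medical Monitor, if use is required. It does not refer to 5.6.2.
- Exclusion 10 opens "Has used any prescription or over-the-counter medication (with exception of acetaminophen" and covers the 14 days before Day 1. Section 5.6.2 covers the same 14 days but does not name acetaminophen.

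All on-study medication goes on the eCRF (5.6.5), and protocol 9.2.8 promises a listing of all medications with dates.

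SAP 7.4.2 summarises observed laboratory values and changes from baseline by treatment at each time point, then says: "Additional Urinary biomarkers include albumin, creatinine, KIM-1, and NGAL will also be listed and summarized similarly". SAP 7.2.5 calls a medication prior if taken before the first dose, and concomitant if taken from then until the last PK sample. It lists and summarises those two categories.

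**The concern.** The study has no control arm, so within-subject change carries most of the weight in judging renal safety. If a subject takes an NSAID and KIM-1, NGAL, urinary albumin or creatinine then moves, a reader needs to see both facts together. The planned outputs do not do that. The renal tables and listings carry no marker of NSAID use. The SAP's medication categories stop at about 48 hours, so use between discharge and the Day 8 or Day 15 sample need not appear in SAP outputs at all. One such subject could make a small cohort's renal summary look worse than the drug warrants, or give a ready alternative explanation for a real drug effect.

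**Working it through.** **Inputs.** Protocol 5.1: "There will be 2 separate and sequential SC cohorts with 4 subjects in each cohort". Randomisation and blinding are not used (5.3), and all subjects receive OP-101. Post-dose biomarker visits are Days 2, 3, 8 and 15 (Appendix A, note 6). The last PK sample is on Day 3, about 48 hours after dosing. The rate of NSAID use is not given anywhere.

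**The plan's own figure.** 2 cohorts × 4 = 8 subjects, as stated in protocol 9.3. The size rests on practical grounds, so there is no power calculation to reproduce.

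**Gap between the two windows (nominal times).**
- Day 8 is 7 × 24 = 168 h after dosing; Day 15 is 14 × 24 = 336 h.
- Time before the Day 8 sample not covered by the SAP definition: 168 − 48 = 120 h, or 5 days.
- Time before the Day 15 sample not covered: 336 − 48 = 288 h, or 12 of the 14 days (288/336 = 86%).
- Two of the four post-dose biomarker visits fall after the window closes.

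**Visits affected, by time of first intake.**
- Before the Day 2 sample: 4 visits.
- Between the Day 2 and Day 3 samples: 3.
- Between the Day 3 and Day 8 samples: 2.
- Between the Day 8 and Day 15 samples: 1.

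**Weight of one user.**
- Share of a cohort's data at a visit: 1/4 = 25%. Share of the study's: 1/8 = 12.5%.
- If the changes from baseline are (0, 0, 0, d), the mean is d/4 = 0.25d. The SD is √{[3(0.25d)² + (0.75d)²]/3} = 0.5d. The median is 0.
- One abnormal value moves the incidence from 0/4 (exact 95% interval 0 to 60%) to 1/4 (1 to 81%).

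**If that user is set apart.** Three subjects remain: 0/3 has an interval of 0 to 71%, and 1/3 has 1 to 91%. A summary without flagged values is therefore even less precise than the full one.

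**Chance that the issue arises.** With an assumed probability p that a subject uses an NSAID on study, P(at least one user among n) = 1 − (1 − p)ⁿ.

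| Assumed p | n = 4 | n = 8 |
|---|---|---|
| 5% | 19% | 34% |
| 10% | 34% | 57% |
| 20% | 59% | 83% |
| 30% | 76% | 94% |

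These rates are illustrative only. They refer to use at any time on study, so the chance of use before any one visit is no higher.

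**The case against.** Several stronger readings are tempting, and the documents do not carry them.

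- **That 5.6.4 overrides 5.6.2.** Section 5.6.4 is conditional (case by case, in consultation, if required) and nothing in it waives the general test. What stands is that the two sections use different wording and name different decision makers, without a cross-reference. The acetaminophen mismatch is confined to the 14 days before dosing.
- **That the SAP pools all renal values.** It does not. It summarises by treatment and visit, tabulates abnormal values and lists the biomarkers. Protocol 9.2.8 promises a dated medication listing, so with 8 subjects a reader could match the two by hand. What stands is that no such link is planned and that the SAP's own definition leaves late use uncategorised.
- **That a renal change after an NSAID cannot be attributed, or would drop out of the stopping rules.** Protocol 8.1.3 requires concomitant drugs to be weighed, and time courses, absolute values and two dose levels also inform the judgement. The definition of related does require that no other cause be identifiable. However, 8.1.1 treats as a reaction anything whose relationship cannot be ruled out, so the documents do not establish that an event would be discounted. Attribution is harder, not impossible.
- **That all four visits and the escalation decision are exposed.** All four are exposed only if intake precedes the Day 2 sample, and use after Cohort 1's Day 8 samples cannot affect the escalation review. The committee also includes the Medical Monitor and the Principal Investigator or delegate, the roles involved in NSAID decisions.
- **That NSAIDs should not have been named, or would mask tolerability symptoms.** The first is a clinical decision outside this review. The documents give no support for the second.

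A further objection stands in full: NSAID use may itself follow a reaction to OP-101, so removing those values could selectively remove affected subjects.

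**Conclusion.** The point holds as a gap in the analysis plan. The protocol names the kidney as a concern and allows NSAIDs to be considered during the study. The SAP neither connects the two nor classifies medication taken after about 48 hours, although half of the post-dose biomarker visits come later. The size is 25% of a cohort's renal data at each visit that follows one subject's use. The conclusion assumes that at least one subject uses an NSAID, at a frequency the documents do not give. It also assumes that NSAIDs can affect renal measures, which is general pharmacology and not stated in either document. It does not show that the renal summaries would be wrong, nor that any medication rule is wrong.

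**What to change.** 1. **Protocol.** The sponsor should reconcile 5.6.4, 5.6.2, exclusion 10 (acetaminophen in the 14 days before dosing) and section 1.2. Which rule should apply is the sponsor's clinical decision.
2. **SAP 7.2.5.** Extend the concomitant-medication window through Day 15. This matches the restriction period in protocol 5.6.2 and the full medication listing in protocol 9.2.8.
3. **SAP 7.4.2.** Using eCRF medication dates, flag in the listings each eGFR, creatinine, KIM-1, NGAL, urinary albumin and urinalysis value obtained after on-study NSAID intake. Show the intake date beside it, because one early intake would flag every later visit. Keep the all-values summary as primary. Add a supportive summary by cohort without flagged values only if any use occurs. State that it may rest on 3 or fewer subjects and that NSAID use may itself follow a drug reaction.

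The cost is a short protocol clarification, a revised definition and a sentence or two in the SAP, a listing flag and, if needed, one extra table. It requires no new data collection and no change in sample size. The drawback is the imprecision of the supportive summary, which cannot settle causality by itself.
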